## 10 Pharmacokinetics Analysis

The pharmacokinetic parameters will be calculated using Noncompartmental Analysis (NCA) SAS macro (version 1.0). In general, the individual and summary tables, using descriptive statistics (N, median, mean, standard deviation, coefficient of variation, minimum, maximum), of pharmacokinetic parameters will be summarized descriptively by treatment formulation. Descriptive statistics for aripiprazole and dehydro-aripiprazole concentration data will be presented.

### 10.1 Primary Pharmacokinetics Endpoint Analyses

The following PK parameters will be estimated and summarized descriptively for aripiprazole:  $C_{56}$  and  $AUC_{0-56}$  of aripiprazole 2M LAI 960 mg after the fourth dose,  $C_{28}$  of aripiprazole IM depot 400 mg after the eighth dose, and the sum of  $AUC_{0-28}$  of aripiprazole IM depot 400 mg after the seventh and eighth dose over the course of 32

Protocol 031-201-00181

weeks. Values for  $AUC_{0-28}$ , and  $AUC_{0-56}$  will be summarized based on samples from subjects enrolled to the robust sampling schedule; whereas  $C_{28}$  and  $C_{56}$  will be summarized based on samples from subjects enrolled to the robust and sparse sampling schedules.

The 90% confidence interval (CI) of GMR of  $C_{56}$  of aripiprazole after the fourth injection of aripiprazole 2M LAI 960 mg (test) to  $C_{28}$  after the eighth injection of aripiprazole IM depot 400 mg (reference) will be provided. An analysis of variance will be performed on the natural-log transformed PK parameters using the MIXED procedure in the Statistical Analysis System (SAS). The mixed-effects linear model will include treatment formulation, disease type (if applicable), and PK sampling schedule (if applicable) as fixed effects and subject as a random effect. The least squares mean for the 2 treatment formulations, their difference, and the 90% CI for their difference will be derived. The antilog of the confidence limits will provide the 90% CI for the GMR of the 2 treatments. For subjects enrolled to the robust sampling schedule, the values of  $AUC_{0-28}$  after the seventh and eighth doses of aripiprazole IM depot 400 mg (reference) will be summed up before analyzing by the same method together with  $AUC_{0-56}$  after the fourth injection of aripiprazole 2M LAI 960 mg (test). Only subjects who receive the fourth dose of aripiprazole 2M LAI 960 mg or the seventh and eighth dose of aripiprazole IM depot 400 mg and have  $C_{56}$ ,  $C_{28}$ ,  $AUC_{0-28}$ , and  $AUC_{0-56}$  values determined for the respective treatments will be included in the analysis.

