CI of GMR of  $C_{56}$  of aripiprazole after the fourth injection of aripiprazole 2M LAI 960 mg (test) to  $C_{28}$  after the eighth injection of aripiprazole IM depot 400 mg (reference) will be provided. An analysis of variance will be performed on the natural-log transformed PK parameters using the MIXED procedure in the Statistical Analysis System (SAS). The mixed-effects linear model will include treatment group, disease type (if applicable), and PK sampling schedule as fixed effects and subject as a random effect. The least squares means for the 2 treatment groups, their difference, and the 90% CI for their difference will be derived. The antilog of the confidence limits will provide the 90% CI for the GMR of the 2 treatments. For subjects enrolled to the robust sampling schedule, the values of  $AUC_{0-28}$  after seventh and eighth doses of aripiprazole IM depot 400 mg (reference) will be summed up before analyzing by the same method together with  $AUC_{0-56}$  after the fourth injection of aripiprazole 2M LAI 960 mg (test). Only subjects who receive a fourth dose of aripiprazole 2M LAI 960 mg or a seventh and/or eighth dose of aripiprazole IM depot 400 mg and have  $C_{56}$ ,  $C_{28}$ ,  $AUC_{0-28}$ , and  $AUC_{0-56}$  values determined for the respective treatments will be included in the analysis.

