## 3 Trial Design

This is a phase 1b, open-label, multiple-dose, randomized, parallel-arm, multicenter (approximately 20 trial sites) trial in adult subjects with schizophrenia or bipolar I disorder. The trial design schematic is shown in [Figure 3-1](#).

Subjects between the ages of 18 to 64 years old, inclusively, are randomized (1:1 randomization) to receive multiple doses of 2 month (2M) long-acting injectable (LAI) 960 mg (4 injections) or aripiprazole IM depot 400 mg (8 injections) over the course of 32 weeks. Aripiprazole 2M LAI 960 mg are administered at 56-day intervals and aripiprazole IM depot 400 mg are administered at 28-day intervals (+/- 2 days). A final visit occurs 56 (+/- 2) days after the last dose of aripiprazole 2M LAI 960 mg or 28 (+/- 2) days after the last dose of aripiprazole IM depot 400 mg. The randomization is

Protocol 031-201-00181

stratified by PK sampling schedules (robust sampling schedule or sparse sampling schedule) and disease type (schizophrenia or bipolar I disorder). If enrollment of the number of subjects required for the robust sampling schedule is completed, the robust sampling trial sites may enroll new subjects to the sparse sampling schedule.

The trial consists of a screening period of up to 30 days, a treatment period of 169 ( $\pm 2$ ) days, and a follow-up period of 56 ( $\pm 2$ ) days after administration of the final dose for the aripiprazole 2M LAI 960 mg treatment group, or a treatment period of 197 ( $\pm 2$ ) days, a follow-up period with 28 ( $\pm 2$ ) days after administration of the final dose for the aripiprazole IM depot 400 mg treatment group. Individual participation is approximately 255 ( $\pm 2$ ) days.

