## 4 Sample Size and Power Justification

To establish the similarity in primary PK variables, the lower bound of the 90% CI of the geometric means ratio (GMR) of  $C_{56}$  and  $AUC_{0-56}$  after the fourth dose of aripiprazole 2M LAI 960 mg to  $C_{28}$  after the eighth dose and the sum of  $AUC_{0-28}$  values after the seventh and eighth doses of aripiprazole IM depot 400 mg should be greater than 80%, respectively.

It is estimated that a total of at least 100 subjects (i.e., 50 per group) completing the trial will have at least 80% power to ensure that the lower limit of the 90% CI of the GMR of  $C_{56}$  after the fourth dose of aripiprazole 2M LAI 960 mg (test) to  $C_{28}$  after the eighth dose of aripiprazole IM depot 400 mg (reference) is greater than 0.80, assuming that the actual GMR of concentrations is 1.0 and the CV is 46%.

Among these 100 subjects, at least 30 completers enrolled to the robust sampling schedule will provide at least 80% power to ensure that the lower limit of the 90% CI of the GMR of  $AUC_{0-56}$  of aripiprazole 2M LAI 960 mg (test) to the sum of  $AUC_{0-28}$  values of aripiprazole IM depot 400 mg (reference) after the seventh and eighth doses is greater than 0.80, assuming the actual GMR of concentrations is 1.15 and the CV is 40%.

The assumption of CV used in the sample calculation is based on the PK data in the previous multiple-dose aripiprazole IM depot PK Trial 31-12-298.

Assuming a dropout rate of 34%, approximately 152 to 258 subjects are estimated to be enrolled to have 100 to 170 completers based on the proposed interim analysis.

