## 5 Statistical Analysis Datasets

The datasets for analyses are defined as the following:

- Randomized sample consists of all subjects who are randomized.
- Safety sample includes all randomized subjects who receive at least 1 dose of aripiprazole injection, regardless of any protocol violation.
- Pharmacokinetics sample consists of all dosed subjects who have 1 or more evaluable aripiprazole PK parameters. For analysis of the primary PK endpoint, only the completers with available values of the primary endpoints after the last scheduled injection are included.
- Efficacy sample includes all randomized subjects who receive at least 1 dose of aripiprazole injection and have at least 1 efficacy assessment.

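### The primary PK model has a random subject effect but only one value per subject, so its two variances cannot be separated and the SE and df behind the 90% CI are left to the software

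*SAP*

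**What the plan says.** SAP 10.1 analyses the natural log of the primary PK parameters with PROC MIXED. The listed effects are treatment formulation, disease type (if applicable) and "PK sampling schedule (if applicable) as fixed effects and subject as a random effect". Protocol 7.4.1 lists "PK sampling schedule as fixed effects and subject as a random effect", and the statistical methods part of the synopsis does the same.

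The remaining text fixes the number of values per subject:

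- **Design.** SAP 3 describes parallel arms, with subjects "randomized (1:1 randomization) to receive multiple doses" of one product or the other.
- **Trough.** SAP 6.2 and 10.1 compare C56 after the fourth 960 mg dose with C28 after the eighth 400 mg dose, which is one value per subject.
- **AUC.** The two reference AUC0-28 values "will be summed up before analyzing by the same method together with" the test-arm AUC0-56, which again leaves one value per subject.
- **Analysis set.** SAP 5 states: "For analysis of the primary PK endpoint, only the completers with available values of the primary endpoints after the last scheduled injection are included".

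No covariance structure, denominator df method or non-convergence rule is given for this model. SAP 9 gives all three for the exploratory efficacy MMRM.

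**The concern.** A random subject effect does useful work when a subject contributes repeated values, as in a crossover. Here it duplicates the residual: each subject has one row, so the model carries two variance components that describe the same deviation.

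The lower limits of these two 90% CIs decide whether similarity is shown (SAP 4). If the model cannot be fitted as specified, someone must decide which term to drop, which df to use, or whether to accept output that carries a warning. The plan does not settle that choice in advance, and the trial is open-label.

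**Working it through.** **1. The plan's own power figures.** Inputs from SAP 4: for C56/C28, 50 per group, GMR 1.0, CV 46%; for AUC, 15 per group, GMR 1.15, CV 40%. The criterion is a lower 90% limit above 0.80, which is one-sided 0.05.

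Formulas: SD of the log = √ln(1 + CV²); δ = ln(GMR/0.80); SE = SD × √(2/n).

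| | C56/C28 | AUC |
|---|---|---|
| SD of log | √ln(1.2116) = 0.4381 | √ln(1.16) = 0.3853 |
| δ | ln(1.25) = 0.2231 | ln(1.4375) = 0.3629 |
| SE | 0.4381 × √(2/50) = 0.0876 | 0.3853 × √(2/15) = 0.1407 |
| Power, normal | 81.6% | 82.5% |

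The stated figure of at least 80% is reproduced for both.

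**2. Identifiability.** With one row per subject, the random-effect design matrix Z is the identity. The covariance of the data is then

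V = σ²(subject) × ZZ′ + σ²(residual) × I = [σ²(subject) + σ²(residual)] × I.

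Only the sum appears. As a numerical check, one trial of each size was simulated at the planning CVs. Two features were assumed: 15 of 50 subjects per arm on robust sampling for C56/C28, and disease type assigned at random. The REML criterion was evaluated with 0, 10, 50, 90 and 99% of the total variance given to subject. Minus twice the log-likelihood was −73.279 at every split for N = 100, and −16.977 at every split for N = 30.

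**3. What remains estimable.** Because V is a multiple of I, generalised least squares reduces to ordinary least squares. In the same simulated trials the treatment estimate did not move across splits, and its SE stayed at the least-squares value (0.0775 and 0.1415). The total variance has N − rank(X) df:

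- C56/C28: intercept, treatment, disease type and schedule give 100 − 4 = 96, t = 1.661.
- AUC: schedule is constant because only robust-schedule subjects enter, so 30 − 3 = 27, t = 1.703.

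In 40,000 simulated trials of each size, 90% limits on these df covered the true value 90.1% and 90.0% of the time.

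**4. Where zero df comes from.** Adding the subject columns saturates the data: rank[X Z] is 100 for N = 100 and 30 for N = 30. A rule that counts df as N − rank[X Z] therefore gives 100 − 100 = 0 and 30 − 30 = 0.

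**5. What software may return.** The model was fitted to simulated data in a general mixed-model routine, not in SAS. It warned that the Hessian was not positive definite and reported SEs of 0.007 against 0.086 by least squares (N = 100) and 0.110 against 0.132 (N = 30). Repeat fits on other simulated trials gave the same warning, with the SE below the least-squares value by varying amounts. PROC MIXED was not run.

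**6. Size if only the reference distribution is in doubt.** The observed GMR needed for the lower limit to reach 0.80 is 0.80 × exp(multiplier × SE), at the planning SE:

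- C56/C28: 0.80 × exp(1.661 × 0.0876) = 0.925 with t; 0.80 × exp(1.645 × 0.0876) = 0.924 with the normal. The difference is about 0.14%.
- AUC: 0.80 × exp(1.703 × 0.1407) = 1.017 with t; 0.80 × exp(1.645 × 0.1407) = 1.008 with the normal. The difference is about 0.8%.

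**7. After the change.** Using the noncentral t on 96 and 27 df, power is 81.2% for C56/C28 and 80.8% for AUC. At the one-sided 0.049 that Protocol 7.1.1 sets if the interim is run, it is 80.9% and 80.5%.

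**The case against.** The strongest defence is that the extra term is harmless. In exact algebra the GMR and its SE are the least-squares values however the variance is divided, and the t-versus-normal difference is under 1% of the limit. Missing limits or zero df would be visible and could not pass as a result. On this view the point is one of wording.

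Much of that stands. It limits three stronger readings that a reader might infer:

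- **No df remain and the CI cannot be obtained.** This holds only under the N − rank[X Z] count. The documents do not prescribe that rule, and a valid CI exists on N − rank(X) df.
- **The CI changes with the split between the two variances.** It does not; step 3 shows the same estimate and SE at every split.
- **The sample size assumes the fixed-effects model.** SAP 4 states only GMR, CV and numbers of completers, and a plain two-group calculation reproduces its power.

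What the defence does not cover is the step from algebra to reported output. In step 5 a routine returned a finite, plausible-looking SE that was too small. An error of that kind could pass as a result.

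SAP Table 5.2-1 might also seem to rescue the term, because it lists a Day 197 window (28 days after the seventh 400 mg injection) among the primary variables. SAP 6.2 and 10.1 restrict the primary comparison to the eighth dose, so one value per subject stands.

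**Conclusion.** The concern holds in this form: the specified primary model is unidentifiable by construction, and the plan does not say how its SE and df are to be obtained. The documents do not support saying that the primary CI is unobtainable, that the GMR is biased, or that power is lost.

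If the software resolves the fit cleanly, the effect on the limit is about 0.14% (C56/C28) to 0.8% (AUC). If it does not, the reported SE or df may be wrong or missing by an amount that cannot be predicted from the documents. PROC MIXED's behaviour under the sponsor's coding is unknown, so the second case is a risk and not a forecast.

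The figures of 96 and 27 df assume 100 and 30 completers with the covariates kept. Disease type and, in the SAP, schedule are included only if applicable, so the C56/C28 df could be 96 to 98 and the AUC df 27 or 28. The defect should be corrected because both decision CIs rest on this model.

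**What to change.** Delete the clause making subject a random effect in SAP 10.1, Protocol 7.4.1 and the synopsis. State instead a fixed-effects linear model on the log value with treatment and disease type, plus sampling schedule for C56/C28 only. Take the confidence limits from the t distribution on N − rank(X) df. The same rule applies unchanged if the sample size is increased: 170 − 4 = 166 df at 170 completers, and 50 − 3 = 47 df at 50 AUC completers.

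The cost is one sentence in three places. Endpoints, visits and sample size are unaffected, and power stays at about 81% for both endpoints.

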## 10.2 Secondary Pharmacokinetics Endpoint Analyses

Individual and summary tables, using descriptive statistics (N, median, mean, standard deviation, coefficient of variation, minimum, maximum) will be provided for the following aripiprazole PK endpoints,

- $C_{max}$  and  $t_{max}$  after the first and fourth doses of aripiprazole 2M LAI 960 mg,
- $AUC_{0-56}$  and  $C_{56}$  after the first dose of aripiprazole 2M LAI 960 mg,
- $AUC_{0-28}$  and  $AUC_{29-56}$  after the fourth dose of aripiprazole 2M LAI 960 mg,
- PTF% after the fourth dose of aripiprazole 2M LAI 960 mg (for aripiprazole only),
- $C_{max}$  and  $t_{max}$  after the first, seventh and eighth doses of aripiprazole IM depot 400 mg,
- $AUC_{0-28}$  and  $C_{28}$  after the first dose of aripiprazole IM depot 400 mg,
- PTF% after the eighth dose of aripiprazole IM depot 400 mg (for aripiprazole only),

Protocol 031-201-00181

- $C_7$  and  $C_{14}$  after the first injection of aripiprazole 2M LAI 960 mg and aripiprazole IM depot 400 mg from subjects enrolled to the robust sampling schedule.

Values for  $C_{max}$ , AUC,  $t_{max}$ , and PTF% will be summarized based on samples from subjects enrolled to the robust sampling schedule; whereas  $C_{28}$  and  $C_{56}$  will be summarized based on samples from subjects enrolled to the robust and sparse sampling schedules.

[REDACTED]

Protocol 031-201-00181

## Appendix 1                      Criteria for Identifying Vital Sign Values of Potential Clinical Relevance

Variable	Criterion Value a	Change Relative to Baseline a
Heart Rate b	> 120 bpm	≥ 15 bpm increase
	< 50 bpm	≥ 15 bpm decrease
Systolic Blood Pressure b	> 180 mmHg	≥ 20 mmHg increase
	< 90 mmHg	≥ 20 mmHg decrease
Diastolic Blood Pressure b	> 105 mmHg	≥ 15 mmHg increase
	< 50 mmHg	≥ 15 mmHg decrease
Orthostatic Hypotension	≥ 20 mmHg decrease in systolic blood pressure and a ≥ 25 bpm increase in heart rate from supine to sitting/standing	Not Applicable
Weight	-	≥ 7% increase ≥ 7% decrease
Temperature	≥ 37.8°C	≥ 1.1°C increase

a In order to be identified as potentially clinically relevant, an on-treatment value must meet the “Criterion Value” and also represent a change from the subject’s baseline value of at least the magnitude shown in the “Change Relative to Baseline” column.

b As defined in “Supplementary Suggestions for Preparing an Integrated Summary of Safety Information in an Original NDA Submission and for Organizing Information in Periodic Safety Updates,” FDA Division of Neuropharmacological Drug Products draft (2/27/87).

Protocol 031-201-00181

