#### 1.4 Risks and Benefits

Abilify Maintena is marketed worldwide and is approved for schizophrenia and bipolar I disorder. To date, no unexpected safety concerns have been reported. The most frequently observed adverse reactions for approved indications are weight increased and akathisia.

Based on a 12-week, double-blind, placebo-controlled trial of Abilify Maintena in adult subjects with schizophrenia, the most commonly observed adverse reactions associated with the use of Abilify Maintena (incidence of 5% or greater and aripiprazole incidence at least twice that for placebo) were increased weight (16.8% versus 7.0%), akathisia (11.4% versus 3.5%), injection site pain (5.4% versus 0.6%), and sedation (5.4% versus 1.2%).

Based on a double-blind, placebo-controlled, randomized withdrawal (maintenance) trial, the most commonly observed adverse drug reactions that were associated with the use of

Protocol 031-201-00181

Abilify Maintena (incidence of 5% or greater and aripiprazole incidence greater than placebo) were weight increased (22.7%) and akathisia (20.5%).

Other commonly reported adverse reactions (reported in 2% or more of Abilify Maintena-treated subjects and at a greater proportion than in the placebo group) during the trials included the following:

- Eye disorders: vision blurred
- Gastrointestinal disorders: constipation, dry mouth, diarrhea, vomiting, and abdominal discomfort
- Infections and infestations: upper respiratory tract infection
- Investigations: decreased weight, blood creatine phosphokinase increased
- Metabolism and nutrition disorders: increased appetite
- Musculoskeletal and connective tissue disorders: arthralgia, back pain, myalgia, and musculoskeletal pain
- Nervous system disorders: dizziness somnolence, sedation, bradykinesis, and tremor
- Psychiatric disorder: anxiety and depression
- Respiratory, thoracic, and mediastinal: nasal congestion
- Reproductive system and breast disorders: erectile dysfunction

In addition to the above, the list of adverse reactions associated with the use of Abilify Maintena or other antipsychotic/atypical antipsychotic drugs includes the following:

- Neuroleptic malignant syndrome
- Tardive dyskinesia
- Metabolic changes that include hyperglycemia/diabetes mellitus, dyslipidemia, and weight gain
- Orthostatic hypotension
- Falls
- Sleep apnea
- Leukopenia, neutropenia, and agranulocytosis
- Impairment of judgment, thinking, or motor skills

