### **3.7.3 Schedule of Assessments**

Subjects are to continue their current oral antipsychotic, mood stabilizer, or antidepressant medications as specified in [Section 3.1](#).

At each time point for vital signs, blood pressure (systolic and diastolic) and heart rate will be taken after subjects have been in the supine position for at least 5 minutes and again after subjects have been standing for 2 minutes, but not more than 3 minutes. Body temperature will be taken with the subject in the supine position (ie, only once). The ECG will be recorded after the subject has been supine and at rest for  $\geq 10$  minutes prior to the

Protocol 031-201-00181

first ECG and subjects will remain supine through the final ECG. Vital signs will be obtained prior to PK blood draws and ECGs at the nominal time points, where applicable, and ECGs will be collected prior to PK blood draws at the nominal time points, where applicable. If a PK blood sample cannot be drawn at the designated postdose times, a window of  $\pm$  15 minutes for each blood draw is acceptable, with the exact time recorded. All efficacy assessments will be performed prior to PK blood draws and dosing, where applicable.

After predose assessments on Day 1, subjects will be randomized 1:1 to receive multiple doses of aripiprazole 2M LAI 960 mg or aripiprazole IM depot 400 mg over the course of 32 weeks.

Whenever a serious adverse event (SAE) occurs, blood samples should be collected as early as is feasible to measure the plasma concentrations of aripiprazole.

Assessments performed at the screening visit are summarized in [Table 3.7.3-1](#).

Assessments are summarized by trial day in [Table 3.7.3-2](#) for subjects enrolled to the sparse sampling schedule and in [Table 3.7.3-3](#) for subjects enrolled to the robust sampling schedule. Trial visits that are 2 days apart should be done in relation to the last dosing (ie, the  $\pm$  2-day window does not apply).

Protocol 031-201-00181

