## 4.2 Restricted Medications

Benzodiazepine use is allowed up to a maximum of 6 mg/day lorazepam or equivalent, but not within 8 hours of any rating scales during the trial. The use of IM lorazepam is also permitted for emergent agitation, but only if deemed absolutely necessary by the investigator. The following guide should be used to determine approximate lorazepam equivalents: 1 mg lorazepam = 5 mg diazepam = 15 mg oxazepam = 15 mg clorazepate. Subjects must not be on more than one benzodiazepine beyond the screening visit.

If a subject is receiving 2 benzodiazepines at the screening visit (eg, lorazepam and oxazepam), attempts should be made to discontinue one of the benzodiazepines, if clinically warranted, to allow potential subjects to enter the trial. The second benzodiazepine should be tapered off over an appropriate amount of time within the

Protocol 031-201-00181

30-day screening period to prevent side effects, and the subject should be maintained on the remaining benzodiazepine for at least 14 days prior to the administration of IMP.

Benzodiazepine and non-benzodiazepine use is allowed during the trial as needed to manage AEs such as agitation, anxiety, sleep disturbance, and insomnia. Combined use of both drug classes (ie, benzodiazepines and non-benzodiazepine sleep aids) as treatment for insomnia is not allowed. Benzodiazepine use should be discontinued as soon as the AE for which it was initiated subsides, as per the investigator's discretion, to avoid any withdrawal effects.

Medications that are restricted during the trial are listed in [Table 4.2-1](#).

| Table 4.2-1 Medications Restricted During the Trial |                                      |   |
|--|--------------------------------------|---|
| Medication  | Screening                     | Treatment Period   |
| Anticholinergics a                              | ≤ 4 mg/day benztropine or equivalent | ≤ 4 mg/day benztropine or equivalent  |
| Propranolol (for akathisia or tremor) b, c      | Maximum 60 mg propranolol per day    | Maximum 60 mg propranolol per day   |
| Benzodiazepines b                               | -                                    | No more than one benzodiazepine and not in combination with other sleep aid medication |

aAnticholinergics are not allowed within 12 hours of any rating scales during any phase of the trial.

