## 8 Safety Analyses

Safety assessments including adverse events (AEs), vital signs, ECGs, clinical laboratory monitoring (serum chemistry, hematology, urinalysis), physical examinations, EPS, VAS scores for pain perception, investigator's assessment of most recent injection site, and suicidality via the C-SSRS will be summarized for the safety sample by treatment formulation and disease type in addition to all treated subjects.

In summarizing the incidence of clinically relevant abnormalities in clinical laboratory results, vital sign measurements and ECG measurements, a subject must have had an evaluation that meets the specified criteria. Incidence rate will be calculated as the number of subjects having at least 1 abnormality in the treatment phase divided by the number of subjects in the safety sample.

Safety data collected during in-clinic visits and virtual visits are summarized together.

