### 8.3 Vital Signs

Vital signs include body temperature in supine position, systolic/diastolic blood pressure in supine and standing position and heart rate. Potential clinically relevant vital sign abnormalities will be listed, the criteria for which are provided in [Appendix 1](#).

Incidences of clinically relevant vital signs abnormalities based on observations during scheduled visits and unscheduled post-baseline visits will be tabulated by treatment formulation and disease type. In addition, vital sign parameters and changes from baseline will be summarized by scheduled visit, treatment formulation and disease type.

If vital sign assessments are repeated for the same trial visit, the last repeat values will be used for production of summary tables. This is accomplished by sorting patient data by visit date and visit time (if applicable) within the same trial visit.

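### SAP Appendix 1 counts a postural systolic fall as orthostatic hypotension only if heart rate also rises by at least 25 bpm, so falls without that rise are left out of the only orthostatic incidence based on measured values

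*SAP*

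**What the plan says.** SAP 8.3 describes the data in these words: "Vital signs include body temperature in supine position, systolic/diastolic blood pressure in supine and standing position and heart rate". It sends the listing and the incidence table of relevant abnormalities to the criteria in Appendix 1. The orthostatic hypotension row there reads "≥ 20 mmHg decrease in systolic blood pressure and a ≥ 25 bpm increase in heart rate from supine to sitting/standing". Its baseline-change column is marked not applicable, and the row offers no diastolic or symptom alternative and no exception for drugs that act on heart rate.

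For entry into the incidence table, SAP 8 says "a subject must have had an evaluation that meets the specified criteria". A subject counts once if at least one abnormality occurs in the treatment phase, and the denominator is the safety sample.

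The other blood-pressure rows of Appendix 1 have no heart-rate condition, but they work differently: "an on-treatment value must meet the “Criterion Value” and also represent a change from the subject’s baseline value". The low-systolic row needs a value below 90 mmHg and a fall of at least 20 mmHg from baseline.

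Protocol 3.7.3 has blood pressure and heart rate taken after at least 5 minutes supine and "again after subjects have been standing for 2 minutes, but not more than 3 minutes". No sitting measurement is scheduled. Protocol 1.4 names "Orthostatic hypotension" among the reactions associated with the product or its class. Protocol Table 4.2-1 has an entry beginning "Propranolol (for akathisia or tremor", capped at 60 mg per day in the treatment period; a footnote lets subjects taking it for heart disease continue under the same cap.

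**The concern.** The row carries the name of a blood-pressure event, but its second condition decides whether a measured fall is counted. A large fall with a modest heart-rate rise is treated as no event. Safety and tolerability is a primary objective (Protocol 2.3.1, SAP 2.1), the reaction is a listed risk, and the paired readings that would show it are collected. At stake is whether the safety tables can say how many subjects on each formulation had a measured postural fall in systolic pressure. As written they cannot.

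The gap may also be uneven across subjects. If propranolol limits the heart-rate rise on standing, which is an assumption and is not stated in either document, its users would meet the criterion less often for the same fall.

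**Working it through.** The documents give no incidence, sensitivity or power figure for this row, so there is no planned figure to reproduce.

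**1. Logic of the rule.** Let A be a supine-to-standing systolic fall of at least 20 mmHg and B a heart-rate rise of at least 25 bpm. The row counts A and B together, and P(A and B) = P(A) × P(B|A) ≤ P(A). The share of falls left out is 1 − P(B|A).

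**2. An example using only Appendix 1 thresholds.** Supine 150 mmHg and 70 bpm; standing 100 mmHg and 85 bpm.
- Systolic fall: 150 − 100 = 50 mmHg, so A is met.
- Heart-rate rise: 85 − 70 = 15 bpm, below 25, so the orthostatic row is not met.
- Standing systolic 100 mmHg is not below 90, so the low-systolic row is not met.
- If diastolic pressure stays at or above 50 mmHg, the low-diastolic row is not met either.

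No hypotension row flags this reading, and no distributional assumption is needed to see it.

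**3. Other outputs.**
- The low-systolic row compares a value with baseline and with 90 mmHg. It does not use the difference between postures.
- The visit summaries, where "vital sign parameters and changes from baseline will be summarized by scheduled visit, treatment formulation and disease type", describe distributions and do not count subjects with a postural fall.
- Orthostasis-related events are tabulated under SAP 8.10. They depend on an event being reported, and Protocol 5.2 elicits events with an open question on how the subject feels.

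**4. Size of the omission, under assumptions.** Neither document gives the distribution of the postural heart-rate change. Assume it is normal with mean m and SD s among readings with A. Then P(B|A) = 1 − Φ((25 − m)/s). Share counted by the row:

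| m (bpm) | s = 6 | s = 8 | s = 10 | s = 12 |
|---|---|---|---|---|
| 5 | 0.0% | 0.6% | 2.3% | 4.8% |
| 10 | 0.6% | 3.0% | 6.7% | 10.6% |
| 15 | 4.8% | 10.6% | 15.9% | 20.2% |
| 20 | 20.2% | 26.6% | 30.9% | 33.8% |
| 25 | 50% | 50% | 50% | 50% |
| 30 | 79.8% | 73.4% | 69.1% | 66.2% |

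The share missed is the complement: about 66% to 100% for means of 5 to 20 bpm, 50% at 25 bpm, and 20% to 34% at 30 bpm. More than half are missed only if the median rise among falls is below 25 bpm.

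**5. From readings to subjects.** Post-baseline vital-sign visits in Protocol Table 3.7-1 (sparse) are Days 8, 15, 22, 29, 36, 43, 50, 57, 85, 113, 141, 169, 176, 183, 190, 197, 204, 211, 218 and 225, which is 20 on 960 mg. Days 36, 43, 50, 176, 183 and 190 apply to 960 mg only, so 400 mg has 20 − 6 = 14.

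Take an illustrative 6.7% of readings with A (fall normal, mean 5, SD 10 mmHg) and P(B|A) = 8.8% (heart-rate rise mean 10, SD 8 bpm, correlation 0.3 with the fall), with the same rates in both arms and independent visits:
- Joint row: 0.067 × 0.088 = 0.0059 per reading. 1 − (1 − 0.0059)^20 ≈ 11% on 960 mg; 1 − (1 − 0.0059)^14 ≈ 8% on 400 mg.
- Systolic-only row: 1 − 0.933^20 ≈ 75% on 960 mg; 1 − 0.933^14 ≈ 62% on 400 mg.

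Within-subject correlation would lower all four figures. The gaps between arms here come from visit counts alone.

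**The case against.** The best defence is that this is a descriptive screen. Requiring a heart-rate response trades sensitivity for specificity, which is a legitimate choice. Other routes remain open: the below-90 mmHg row is not confined to supine readings, so it can catch some low standing pressures; standing values are summarised by visit; and orthostasis-related events have their own table. A systolic-only row could flag a large share of subjects and, on unequal visit schedules, suggest a difference between arms where none exists. All of this stands, and it limits the claim: falls are missing from the orthostatic row, not necessarily from every output. It does not close the gap, since none of these routes gives an incidence of supine-to-standing falls.

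Three stronger readings are tempting, and the documents support none of them.

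- A reader might infer that most postural falls are missed. That depends on a heart-rate distribution that is not given, and it reverses if the typical rise among falls exceeds 25 bpm.
- A reader might infer that the incidence will be near zero in both arms by construction. Subjects are counted on any visit, so even a low per-reading rate accumulates, as the 11% and 8% above show.
- A reader might infer that subjects treated for akathisia cannot meet the criterion. The protocol only permits propranolol; it does not say how many will take it or what it does to the postural heart rate.

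The absence of the regulatory-source footnote from this row is not evidence of a fault, because the weight and temperature rows lack it too.

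**Conclusion.** The point holds in a limited form. That the row excludes systolic falls of any size when heart rate rises by less than 25 bpm follows from the text alone. So does the absence of any other planned count of postural falls from measured values. How many falls are lost is unknown: the range in step 4 rests wholly on assumed normal distributions, and preferential loss among propranolol users is plausible but rests on pharmacology outside the documents. The consequence is an incomplete description of one listed risk within a primary safety objective. It is worth correcting because the data are already being collected. The mention of sitting in the criterion is an editorial mismatch with the protocol's supine and standing readings and does not change how the rule applies.

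**What to change.** 1. In SAP Appendix 1, keep the joint row and add a second one that counts a supine-to-standing systolic fall of at least 20 mmHg regardless of heart rate. This reuses the row's own pressure threshold.
2. Under SAP 8.3, list and tabulate the new row by treatment and disease type. Base the subject-level incidence on vital-sign visits scheduled in both arms (the 14 common visits in the sparse schedule), or report it per visit with the number measured as denominator. The robust schedule also needs this: Protocol Table 3.7-2 has three visits for 960 mg only (Days 36, 43, 50) and six for 400 mg only (Days 198, 199, 201, 206, 209, 214).
3. Change sitting/standing to standing, to match the protocol.

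The cost is one more row in the appendix and one in the table, with no new measurement or visit. More subjects will be flagged, some without symptoms; showing both rows side by side makes that visible. A split by propranolol use would be optional, and would be the only way to examine that question in the trial's own data.
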